9.1 Analysis sets

The following analysis sets will be used for the statistical analyses:

The full analysis set (FAS) will consist of all randomized patients with the exception of those patients who have not been qualified for randomization and have not received study drug, but have been inadvertently randomized into the study. Following the intent-to-treat principle, patients will be analyzed according to the treatment to which they were assigned at randomization. Efficacy variables will be analyzed based on the FAS as the primary population.

The Safety (SAF) Population will consist of all randomized patients who received at least one dose of study drug. Patients will be analyzed according to the treatment actually received. The safety population will be used for the analyses of safety variables.

The Per-protocol set (PPS) will be a subset of the FAS which will consist of the patients who do not have major deviations from the protocol procedures in the randomized treatment epoch. Major protocol deviations will be pre-specified prior to unblinding treatment codes for analyses. This supplemental efficacy population will be used to support the primary analysis results.

9.2 Patient demographics and other baseline characteristics

Baseline value is defined as the last non-missing assessment prior to the first dose of randomized study drug unless specified otherwise. This baseline is the randomized treatment epoch baseline.

Summary statistics will be provided by treatment group for demographics and baseline characteristics, including age, age group (<65 years vs. ≥65 years; <75 years vs. ≥75 years), sex, race, ethnicity, weight, height, body mass index (BMI), category of prior CV medication, prior HF hospitalization, NYHA class, NT-proBNP, and vital signs. BMI will be calculated as weight (kg) / height² (m²) from the collected height and weight at Visit 1 (Screening Visit). Continuous variables will be summarized using n, mean, standard deviation, median, minimum, and maximum. Categorical variables will be summarized using frequency and percentage.

The difference between treatment groups will be compared using the Chi-square test for categorical variables or using t-test for continuous variables. The p-values will be provided for descriptive purposes and will not be considered to define any formal basis for determining factors to be included in statistical models. If a substantial imbalance of treatment groups with respect to some variables does occur, supplemental analyses with addition of these variables in model may be performed to assess the potential impact on efficacy as appropriate.

The FAS will be the patient population for the above analyses.

9.3 Treatments

The overall duration on the randomized study drug will be summarized by treatment group using mean, standard deviation, median, minimum, and maximum. Additionally, the number and percentage of patients will be summarized by treatment group for duration category. Mean doses and dose levels will be summarized by treatment group and visit.

Concomitant medications and significant non-drug therapies, prior to and after the randomization date respectively, will be summarized by therapeutic class, preferred term, and treatment group for the safety population.

The number and percentage of patients on different CV background medications (e.g., mineralocorticoid receptor antagonist, β-blockers, diuretics, and digoxin) will be tabulated by treatment at baseline and during the randomized treatment epoch.

The FAS will be used for the above analyses unless otherwise specified.

9.4 Analysis of the primary and secondary variable(s)

9.4.1 Variable(s)

The primary and secondary objectives of this study are presented in [Section 2.1](#) and [Section 2.2](#)

The primary efficacy variable is the cumulative number of primary composite events, i.e., the composite events of (total) HF hospitalizations and CV death, for a given subject, over time.

The secondary efficacy variables are:

1. Change from baseline in KCCQ clinical summary score for HF symptoms and physical limitations at Month 8.
2. Change from baseline to Month 8 NYHA class.
3. Time to first occurrence of the composite renal endpoint, defined as follows:
 - renal death, or
 - reaching ESRD, or
 - $\geq 50\%$ decline in eGFR relative to baseline
4. Time to all-cause mortality.

The time point of Month 8 is defined as Week 32 in accordance with the assessment schedule ([Table 6-1](#)).

9.4.2 Statistical model, hypothesis, and method of analysis

9.4.2.1 Primary analysis

The primary efficacy endpoint of the study consists of the times to recurrent hospitalization due to heart failure and death time due to CV reasons during the patient's follow-up. The comparisons between two treatment groups will be made using statistical procedures which deal with such multiple event time observations. For example, the semi-parametric proportional rates model (abbreviated as LWYY model) ([Lin et al 2000](#)) can be utilized for quantifying the treatment difference.

Specifically, let $\lambda_{ij}(t, x_{ij})$ be the individual rate of primary composite events for subject i in region j , given the patient has not died from a CV reason at time t . It is dependent on time from randomization (t) and treatment group (x_{ij}). Let $x_{ij}=1$ if the subject is in the LCZ696 group and $x_{ij}=0$ if the subject is in the valsartan group.

Under the proportional rates model, the individual rate function for the composite endpoint of CV death and total HF hospitalizations is assumed to be, $\lambda_{ij}(t, x_{ij}) = Y_{ij}(t)\lambda_{0j}(t) \exp(\beta_0 x_{ij})$, where $Y_{ij}(t)=1$ if subject i in region j is at risk for HF hospitalization or CV death at time t and $Y_{ij}(t)=0$ if subject i in region j is censored or died from a CV reason at time t^- and $\lambda_{0j}(t)$ is the baseline rate function for the event in region j .

The primary hypothesis to be tested is, $H_{10}: \beta_0 \geq 0$ versus $H_{1a}: \beta_0 < 0$, where $\exp(\beta_0)$ is the relative risk or rate ratio (RR) of total hospitalizations for HF and CV death in the LCZ696 group relative to the valsartan group given the patient has not died from a CV reason at time t , which is assumed to be constant over time and across regions.

The primary hypothesis could be equivalently written as:

H_{10} : Rate ratio LCZ696/valsartan ≥ 1 versus H_{1a} : Rate ratio LCZ696/valsartan < 1 ,

A rate ratio < 1 indicates an effect in favor of LCZ696.

Note that $\exp(\beta_0)$ can also be considered as a ratio of two mean cumulative frequencies of a subject having hospitalizations for HF and CV death when the rate ratio is constant over time and CV mortality is balanced between treatment groups.

The primary hypothesis will be tested at a one-sided significance level of 0.02499 adjusted for interim analysis. The rate ratio and its 95% confidence interval will be estimated from the above proportional rates model through maximization of a partial likelihood score function. The resulting estimate of $\exp(\beta_0)$ is identical to the one described by Anderson and Gill (Anderson and Gill 1982), but unlike Anderson-Gill, a robust variance estimator (sandwich estimator) is used to account for the dependency of within subject events. Note that having CV death is not considered as a censoring variable, but as a primary endpoint event and a conditional factor in this analysis. Time to non-CV death will be considered as a censoring variable. Any censoring due to non-CV death is assumed to be non-dependent in the analysis.

The above presented analysis method based on LWYY provides a treatment comparison based on primary endpoint rate ratio conditional on not having died from a CV reason. A marginal interpretation of the estimates requires that any censoring of the primary composite events will be non-informative and may be challenging if there is an imbalance in CV mortality.

As a part of the primary analysis, the two components in the composite endpoint (total HF hospitalizations and CV mortality) will be analyzed separately to quantify the respective treatment effects and check the consistency between the composite and the components.

For the analysis of total HF hospitalizations component, occurrence of CV death can be regarded as semi-competing risk (informative censoring) and may introduce a bias in the treatment effect estimate for HF hospitalizations (dilution of effect size if the drug has a positive effect on both components). In order to address this concern and to account for the correlation between the two components, the joint modeling (frailty model) approach (Cowling et al 2006) will be used for the component analyses. The joint model is specified as follows.

$$\begin{aligned}\lambda_{ij}^H(t) &= Y_{ij}(t)\lambda_0^H \exp(\beta_0 x_{ij})v_{ij} \\ \lambda_{ij}^T(t) &= Y_{ij}(t)\lambda_0^T \exp(\gamma_0 x_{ij})v_{ij}^\alpha \\ v_{ij} &\sim f(\cdot)\end{aligned}$$

where $\lambda_{ij}^H(t)$ is the rate function of the total hospitalizations for HF for subject i in region j and λ_0^H is its constant baseline and $\lambda_{ij}^H(t)$ has a similar format as the model described above for the primary endpoint except for the multiplier v_{ij} that is a subject-specific random effect factor (frailty); and $\lambda_{ij}^T(t)$ is the hazard function for the component of CV mortality for

subject i in region j and λ_{0j}^T is its constant baseline and $\lambda_{ij}^T(t)$ is a frailty Cox proportional hazards model. The parameter α measures the association between $\lambda_{ij}^H(t)$ and $\lambda_{ij}^T(t)$. The frailty distribution $f(\cdot)$ will be pre-specified prior to the unblinding of the treatment codes. The parameters in the joint model, including the unknown power for the frailty, will be estimated through maximization of the corresponding likelihood. The model assumes that the correlation between total HF hospitalizations and CV death for each patient is completely explained by the covariates and the frailty and the two analysis variables corresponding to the two components are independent given the patient's frailty and covariates.

For the analysis of CV death, it will be analyzed using Cox's proportional hazards model with a fixed treatment group factor and stratified by region. The analysis in the joint frailty model for this component will be considered as supportive whenever an inference is needed for it.

In all the proposed analyses, it is acknowledged that the study will not be powered to achieve statistically significant results for the CV death. The inference on the total HF hospitalizations can only be made when both the composite endpoint and the total HF hospitalizations itself showed statistically positive results.

Non-parametric estimates of HF hospitalization rates over time allowing for death as terminal event will be provided as well (Ghosh and Lin 2000).

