--	--

Investigational and reference therapy	
LCZ696 50 mg (dose level 1), 100 mg (dose level 2), 200 mg (dose level 3)
 
Valsartan 40 mg (dose level 1), 80 mg (dose level 2), 160 mg (dose level 3)

Efficacy assessments	
 • CV death • Total HF hospitalizations • KCCQ clinical summary score for HF symptoms and physical limitations scores at 8 months • NYHA functional classification at 8 months • Composite renal endpoint • All-cause mortality
Safety assessments	
 • AEs and SAEs • Sitting systolic BP, sitting diastolic BP, and heart rate • Laboratory values (including monitoring for hyperkalemia, renal dysfunction) • ECG changes • Angioedema surveillance
Other assessments	
 • Total non-fatal MIs • Total non-fatal strokes • Resource utilization • Health-related Quality of Life 
 ○ KCCQ overall summary score and subdomain scores; KCCQ clinical summary score relative to the beginning of run-in epoch (in the subset of patients in whom KCCQ assessment was collected at that point) and relative to randomization ○ Clinical composite assessment ○ EuroQol (EQ-5D) • New onset of atrial fibrillation (NOAF) • Echocardiography parameters • Pharmacokinetics • Pharmacogenetics/Pharmacogenomics • Biomarkers • Mini-Mental State Examination score
Data analysis	
The primary efficacy variable is the cumulative number of primary composite endpoint events for a given patient, over time during the double blind period of the study.
 
The secondary efficacy variables are:
 
 • Change in KCCQ clinical summary score from baseline to Month 8 • Change in NYHA class from baseline to Month 8 • Time to composite renal endpoint • Time to all-cause mortality 
Note: randomized treatment epoch baseline is used in the secondary efficacy analysis
 
The primary efficacy analysis will be using a proportional conditional rates model based on cumulative, recurrent events approach analyzing CV

	
death and HF hospitalizations. The primary hypothesis will be tested at a one-sided significance level of 0.024 adjusted for interim analysis (IA).
 
One efficacy interim analysis is planned when approximately two-thirds of the target number of adjudicated primary events is obtained.

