9.6 Interim analyses

One interim analysis for efficacy is planned. The cut-off time for this interim analysis will be when about two-thirds of the target number of primary events have been reported and adjudication-confirmed, approximately 1231 of adjudication-confirmed composite of hospitalizations for HF and CV death. In the interim analysis, the analysis dataset will comprise all patients who were randomized before the cutoff date. Bonferroni multiplicity adjustment will be adopted for the statistical comparisons between treatments. An alpha of 0.001 (one-sided alpha) will be spent for the comparison of primary endpoint at the interim analysis and the rest of alpha (one-sided 0.024 for the current specified boundary) will be utilized for it at the final analysis. In the interim analysis, the study may be stopped for superior efficacy only when the primary endpoint and CV death both are significant at level of 0.001 (one-sided).

If the study is stopped early for claiming superior efficacy at the interim analysis, the secondary endpoints will be tested using the same hierarchical testing procedure as described before with an overall alpha level used for the primary endpoint at the interim analysis (one-sided alpha of 0.001 for the current specified boundary).

Interim safety assessments are planned to be performed every six months. No further alpha adjustment will be made for these interim safety assessments.

Interim analyses will be performed by an independent statistician who will not be involved in the trial conduct. The results will be reviewed by the independent DMC.

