In [Table 9-1](#), sample sizes and powers are estimated through simulations for the framework defined above. Three thousand trial replicates are generated for each scenario with different sample sizes in the simulations. Both the power and type I error rate are estimated for the selected proportional rates model (LWYY). For our study, with a one-sided alpha level of 0.025, a total of 4600 patients will provide more than 90% of power for the LWYY method. This will require approximately 1847 primary events (see the row in table below with sample size = 4600 and HR = 0.9 and RR = 0.7). The type I error rates were preserved well in the cases we examined.

Table 9-1 Sample size and power estimations through simulations

Sample size	Simulation specs		Expected no. of composite events	Estimated HR or RR		Power
	HR for death	RR for total hosp for HF		Time to 1 st composite event	LWYY	
4600	0.9	0.7	1847	0.859	0.778	0.95
		0.75	1882	0.881	0.814	0.85
	1.0	0.7	1846	0.876	0.784	0.94
		0.75	1885	0.900	0.822	0.82

3000 simulation runs were performed for each scenario.

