The primary hypothesis will be tested at a one-sided significance level of 0.024 adjusted for the interim analysis. The rate ratio and its 95% confidence interval will be estimated from the above proportional rates model through maximization of a partial likelihood score function. The resulting estimate of $\exp(\beta_0)$ is identical to the one described by Anderson and Gill ([Anderson and Gill 1982](#)), but unlike Anderson-Gill, a robust variance estimator (sandwich estimator) is used to account for the dependency of within subject events. Note that having CV death is not considered as a censoring variable, but as a primary endpoint event and a conditional factor in this analysis. The “conditional factor” means that the rate of the composite endpoint at time t is evaluated conditional on the patient being at risk of CV death at time t . Time to non-CV death will be considered as a censoring variable. Any censoring due to non-CV death is assumed to be non-dependent in the analysis.

The above presented analysis method based on LWYY provides a treatment comparison based on primary endpoint rate ratio conditional on not having died from a CV reason. A marginal interpretation of the estimates requires that any censoring of the primary composite events will be non-informative and may be challenging if there is an imbalance in CV mortality.

The LWYY analysis can be carried out using the following SAS code:

```
proc phreg data=primary_data covs(aggregate);  
    model (time_start, time_rec)*status_rec(0)=treat/ties=efron rl;  
    id sidla;  
  
run;
```

where `primary_data` is the input dataset, `time_start` is the previous event stop time and `time_rec` is the current event stop time, the censoring variable `status_rec` (0 for censored

and 1 for event) should take the value 1 if the last event is a CV death and 0 if it is censored for any non-CV death reasons for the given patient; `sid1a` is the subject ID.

As a supportive part of the primary analysis, the two components in the composite endpoint (total HF hospitalizations and CV mortality) will be analyzed separately to quantify the respective treatment effects and check the consistency between the composite and the components.

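### Protocol 9.4.2.1 gives the final one-sided level for the primary test as 0.02499; the protocol synopsis, Protocol 9.6 and the SAP give 0.024, the only value that fits the declared alpha split

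*Protocol*

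**What the plan says.** Four places in the current text give the level of the final primary test.

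- Protocol 9.4.2.1, Primary analysis: "The primary hypothesis will be tested at a one-sided significance level of 0.02499 adjusted for interim analysis".
- Protocol synopsis, Data analysis: "The primary hypothesis will be tested at a one-sided significance level of 0.024 adjusted for interim analysis (IA)".
- Protocol 9.6, Interim analyses: the interim look at the primary endpoint uses up 0.001 one-sided. For the final, the section says: "the rest of alpha (one-sided 0.024 for the current specified boundary) will be utilized for it at the final analysis". The method is named there too: "Bonferroni multiplicity adjustment will be adopted for the statistical comparisons between treatments".
- SAP 9.3.1.1: "The primary hypothesis will be tested at a one-sided significance level of 0.024 adjusted for the interim analysis". SAP 9.3.2.1 (step 1 of the testing procedure) and SAP 12 also use 0.024.

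The overall level is one-sided 0.025, as used in the sample size section (Protocol 9.7.1): "with a one-sided alpha level of 0.025, a total of 4600 patients will provide more than 90% of power for the LWYY method".

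Protocol 9.6 and SAP 12 also restrict the interim stop: "the study may be stopped for superior efficacy only when the primary endpoint and CV death both are significant at level of 0.001 (one-sided)".

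**The concern.** The protocol's sentence on the primary test and its section on the interim analysis disagree about the threshold that decides the trial. Both are operative text; neither is an amendment summary.

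A final one-sided p between 0.024 and 0.02499 would be a success under one section and a failure under the synopsis, Protocol 9.6 and the SAP. The secondary hypotheses are tested only if the primary is rejected, so the same ambiguity carries into them. A choice between the two values made after the data are seen would be open to the charge that the result drove it.

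**Working it through.** **Inputs.** Interim level 0.001 and final level 0.024 (Protocol 9.6); final level 0.02499 (Protocol 9.4.2.1); overall level 0.025 (Protocol 9.7.1); 1231 events at the interim (Protocol 9.6) and 1847 at the final (Protocol 3.1). The correlation between the interim statistics for the primary endpoint and CV death is not in the documents, so it is varied.

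**1. The plan's own figure.** Under a Bonferroni split, final level = overall level − interim level = 0.025 − 0.001 = 0.024. This reproduces Protocol 9.6 exactly.

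**2. The challenged figure under the same rule.** 0.001 + 0.02499 = 0.02599, which is 0.00099 above 0.025.

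**3. Width of the disputed zone.** The critical z is 1.9774 at 0.024 and 1.9601 at 0.02499.

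**4. True type I error if the interim stopped on the primary endpoint alone.** The Bonferroni sum is only an upper bound, because the two looks share data.

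- Information fraction t = 1231/1847 = 0.6665; correlation of interim and final statistics √t = 0.816.
- Type I error = a₂ + P(Z₁ > c₁, Z₂ ≤ c₂), where a₂ is the final level, c₁ = 3.090 (upper 0.001 point) and c₂ is the final critical value.
- With a₂ = 0.024: 0.02400 + 0.00010 = 0.02410.
- With a₂ = 0.02499: 0.02499 + 0.00010 = 0.02509.
- The largest final level that holds 0.025 exactly under this rule is 0.02490.

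**5. True type I error under the stated stopping rule.** Let D be the interim CV death statistic and ρ its correlation with Z₁. The formula becomes a₂ + P(Z₁ > c₁, D > c₁, Z₂ ≤ c₂). D is taken to relate to Z₂ only through Z₁, and CV death is taken to have no treatment effect.

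| Assumed ρ | Final level 0.024 | Final level 0.02499 |
|---|---|---|
| 0 | 0.02400 | 0.02499 |
| 0.5 | 0.02400 | 0.02499 |
| 0.6 | 0.02401 | 0.02500 |
| 0.7 | 0.02401 | 0.02500 |
| 0.9 | 0.02404 | 0.02503 |

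Unrounded, the 0.02499 column is 0.024998 at ρ = 0.6 and 0.025003 at ρ = 0.7, so it crosses 0.025 between them. If ρ were 1, or if CV death were certain to pass at the interim, the result returns to step 4 (0.02509). That is the ceiling.

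**6. Effect on power.** Standard errors were backed out of the powers in Protocol Table 9-1, which are stated at 0.025. Using 0.024 instead takes 0.95 to 0.948, 0.94 to 0.938, 0.85 to 0.846 and 0.82 to 0.815. Each loss is below half a percentage point, so the sample size does not depend on this point.

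**The case against.** **The SAP has already settled it.** Protocol Section 9 describes itself as a preliminary approach. The SAP is later and more detailed, and uses 0.024 in every operative place. Its document history records that this same 0.02499 was corrected to 0.024 in the version dated September 2016, well before the 30 April 2019 cut-off. This largely stands: an analyst following the SAP would use 0.024. It does not remove the contradiction inside the protocol. SAP Section 1 says the data will be analysed according to the protocol's data analysis section, and neither document says that the SAP prevails where they differ.

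**No sum in the plan is wrong.** This also stands: 0.001 + 0.024 = 0.025 in Protocol 9.6 is correct. The point is one of consistency. The SAP history gives the earlier interim boundary as 0.0001, and a 0.0001 look at half the events leaves a final level of about 0.02499. A carry-over is therefore plausible, but that is inference and the point does not need it.

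**The stronger reading.** A reader might infer from 0.02599 that the trial would fail to control one-sided error at 0.025 if 0.02499 were applied. The documents do not support that as a material claim. The sum is a bound, not the error rate. Even the 0.0251 figure assumes a stop on the primary endpoint alone, and the plan also requires CV death to reach 0.001.

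**Conclusion.** Protocol 9.4.2.1 states a final level that conflicts with the synopsis, Protocol 9.6 and the SAP, and that does not fit the Bonferroni split the protocol declares. That follows from the text and needs no assumption.

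The size is small. The decision differs only for a final one-sided p in a window 0.00099 wide. True type I error at 0.02499 exceeds 0.025 by at most about 0.00009 (primary-only stopping). Under the stated rule it exceeds it by about 0.00003 at an assumed ρ of 0.9, and not at all up to about ρ = 0.6. These error rates rest on jointly normal statistics, an information fraction equal to the event fraction, and the assumptions in step 5. This is an unreconciled primary decision threshold. It is worth correcting because a threshold must be unique before unblinding, not because error control is materially at risk.

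**What to change.** Replace 0.02499 with 0.024 in Protocol 9.4.2.1, so that it agrees with the synopsis, Protocol 9.6 and SAP 9.3.1.1. If no further protocol amendment is made, add one sentence to the SAP before unblinding stating that 0.024 supersedes the 0.02499 in Protocol 9.4.2.1.

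The cost is one number or one sentence. No analysis, boundary, sample size or event target changes.
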